10.2 Stopping Rule

Based on preclinical data, we do not believe the TBI at such a low-dose will aggravate GVHD, and we do not expect additional regimen-related toxicities at this dose. Patients will not be enrolled into Stage 2 until all patients in Stage 1 have reached 90 days post-transplant. Patients will not be enrolled into Stage 2 until all patients in Stage 1 have reached 90 days post-transplant.

The study will be terminated if the number of subjects who experience a "stopping event" (defined as Grade 4 GVHD) is 2, 3 or 4 among (respectively) the first 6, 12, or 18 patients. This rule is based on stopping if the lower 80% confidence limit for the true probability of a "stopping event"

exceeds 12% (the maximal acceptable rate) at any look. The rule is implemented with a forward-looking interpretation, so that if the number of events hits the boundary for the current look at any time, the study will stop. Subjects will not be enrolled into Stage 2 until all subjects in Stage 1 have reached 90 days post-transplant without triggering the stopping rule, and enrollment will be delayed if necessary at each stopping rule milestone, to ensure that subject 7, 13, and 19 are not enrolled until the stopping rule at (respectively) 6, 12, and 18 is cleared (for example, if there has been one stopping event in the first 5 subjects, enrollment is paused until patient 6 reaches 90 days without an event).

The stopping rule described above, which we have used in many studies, controls the "false alarm" rate. We do not generally calculate the "true alarm rate" at probabilities exceeding the max acceptable rate, because we do not think it is informative. It is well-understood that the small samples in phase 1 and 2 generally do not provide precise upper bounds for the probability of unwanted effects, so the purpose of stopping rules is to protect the patients enrolled in the study, as far as possible, consistent with the inherent risks of early phase studies and the potential benefit. If the stopping rule is not triggered even though the true risk is substantially greater than the max acceptable rate, then the actual harm has been limited to the extent possible in an early phase trial.

10.3 Sample Size

Twenty patients will be required to complete the study.

10.4 Accrual estimates

Approximately 10 to 15 patients will be enrolled annually. Time to complete enrollment will be 2 years. Overall time to initiate, conduct, and complete the trial will be about 4 years.

APPENDIX A: Glucksberg clinical stage and grade of acute GVHD

Stage	Skin	Liver	Intestinal tract
1	Maculopapular rash < 25% of body surface	Bilirubin 34–50 µmol/l	> 500 ml diarrhoea/d
2	Maculopapular rash 25–50% body surface	Bilirubin 51–102 µmol/l	> 1000 ml diarrhoea/d
3	Generalized erythroderma	Bilirubin 103–225 µmol/l	> 1500 ml diarrhoea/d
4	Generalized erythroderma with bullous formation and desquamation	Bilirubin > 255 µmol/l	Severe abdominal pain, with or without ileus

Grade	Degree of organ involvement
I	Stage 1–2 skin rash; no gut involvement; no liver involvement; no decrease in clinical performance
II	Stage 1–3 skin rash; stage 1 gut involvement or stage 1 liver involvement (or both); mild decrease in clinical performance
III	Stage 2–3 skin rash; stage 2–3 gut involvement or 2–4 liver involvement (or both); marked decrease in clinical performance
IV	Similar to Grade III with stage 2–4 organ involvement and extreme decrease in clinical performance

APPENDIX B. RESPONSE CRITERIA by DISEASE HISTOLOGY

AML Response Criteria (Cheson, et al. 2003)

Response Criterion	Time of Assessment	Neutrophils (μ L)	Platelets (μ L)	Bone Marrow Blasts (%)	Other
Early treatment assessment	7-10 days after therapy	NA	NA	< 5	
Morphologic leukemia-free state	Varies by protocol	NA	NA	< 5	Flow cytometry EMD
Morphologic CR	Varies by protocol	> 1,000	> 100,000	< 5	Transfusion EMD
Cytogenetic CR	Varies by protocol	> 1,000	> 100,000	< 5	Cytogenetics – normal, EMD
Molecular CR	Varies by protocol	> 1,000	> 100,000	< 5	Molecular – negative, EMD
Partial remission	Varies by protocol	> 1,000	> 100,000	> 50 or decrease to 5-25	Blasts < 5% if Auer rod positive

In this study Day of assessment is 12 weeks and 24 weeks post stem cell infusion. For patients who are in a pathologically confirmed remission prior to infusion, a bone marrow biopsy and/or aspirate are not required; disease can be followed by confirmatory CBCs

NHL Response Criteria (Cheson, et al. 2007)

Response	Definition	Nodal Masses	Spleen, Liver	Bone Marrow
CR	Disappearance of all evidence of disease	(a) FDG-avid or PET positive prior to therapy; mass of any size permitted if PET negative (b) Variably FDG-avid or PET negative; regression to normal size on CT	Not palpable, nodules disappeared	Infiltrate cleared on repeat biopsy; if indeterminate by morphology, immunohistochemistry should be negative
PR	Regression of measurable disease and no new sites	≥ 50% decrease in SPD of up to 6 largest dominant masses; no increase in size of other nodes (a) FDG-avid or PET positive prior to therapy; one or more PET positive at previously involved site (b) Variably FDG-avid or PET negative; regression on CT	≥ 50% decrease in SPD of nodules (for single nodule in greatest transverse diameter); no increase in size of liver or spleen	Irrelevant if positive prior to therapy; cell type should be specified
SD	Failure to attain CR/PR or PD	(a) FDG-avid or PET positive prior to therapy; PET positive at prior sites of disease and no new sites on CT or PET (b) Variably FDG-avid or PET negative; no change in size of previous lesions on CT		
Relapsed disease or PD	Any new lesion or increase by ≥ 50% of previously involved sites from nadir	Appearance of a new lesion(s) > 1.5 cm in any axis, ≥ 50% increase in SPD of more than one node, or ≥ 50% increase in longest diameter of a previously identified node > 1 cm in short axis. Lesions PET positive if FDG-avid lymphoma or PET positive prior to therapy.	> 50% increase from nadir in the SPD of any previous lesions	New or recurrent involvement

In this study, the day of assessment is 12 weeks and 24 weeks after stem cell infusion.

CLL Response Criteria (Hallek, et al. 2008)

Parameter	CR	PR	PD	SD
Lymphadenopathy ¹	None above 1.5 cm	Decrease \geq 50%	Increase \geq 50%	Change of -49% to +49%
Liver and/or spleen size	Normal size	Decrease \geq 50%	Increase \geq 50%	Change of -49% to +49%
Constitutional symptoms	None	Any	Any	Any
Polymorphonuclear leukocytes	> 1500/ μ L	> 1500/ μ L or > 50% improvement over baseline	Any	Any
Circulating clonal B-lymphocytes	Nil	Decrease \geq 50% from baseline	Increase \geq 50% from baseline	Change of -49% to +49%
Platelet count	> 100,000/ μ L	> 100,000/ μ L or increase \geq 50% over baseline	Decrease of \geq 50% from baseline secondary to CLL	Change of -49% to +49%
Hemoglobin	> 11.0 g/dL (untransfused and without erythropoietin)	> 11 g/dL or increase \geq 50% over baseline	Decrease of > 2 g/dL from baseline secondary to CLL	Increase < 11.0 g/dL or < 50% over baseline, or decrease < 2 g/dL
Marrow	Normocellular, < 30% lymphocytes, no B-lymphoid nodules. Hypocellular marrow defines CRi.	\geq 30% lymphocytes, or B-lymphoid nodules, or not done	Increase of lymphocytes to more than 30% from normal	No change in marrow infiltrate

¹ sum of the products of multiple lymph nodes (as evaluated by CT scans, physical exam or ultrasound).

CR: complete remission, all of the criteria have to be met, with a marrow aspirate and biopsy performed at least 3 months after last treatment;
 PR: partial remission, at least one of the criteria has to be met; PD: progressive disease, at least one of the above criteria has to be met; SD: stable disease, all of the above criteria have to be met. Note that it is not necessary to assess bone marrow to confirm SD and determination of circulating clonal B lymphocytes is only necessary if other criteria are insufficient to define a response.

In this study day of assessment is 12 weeks and 24 weeks post stem cell infusion.

MDS Response Criteria (Cheson, et al. 2006)

Category	Response criteria (responses must last at least 4 wk)
Complete remission	Bone marrow: $\leq 5\%$ myeloblasts with normal maturation of all cell lines* Persistent dysplasia will be noted† Peripheral blood‡ Hgb ≥ 11 g/dL Platelets $\geq 100 \times 10^9/L$ Neutrophils $\geq 1.0 \times 10^9/L$ † Blasts 0%
Partial remission	All CR criteria if abnormal before treatment except: Bone marrow blasts decreased by $\geq 50\%$ over pretreatment but still $> 5\%$ Cellularity and morphology not relevant
Marrow CR†	Bone marrow: $\leq 5\%$ myeloblasts and decrease by $\geq 50\%$ over pretreatment† Peripheral blood: if HI responses, they will be noted in addition to marrow CR†
Stable disease	Failure to achieve at least PR, but no evidence of progression for > 8 wks
Failure	Death during treatment or disease progression characterized by worsening of cytopenias, increase in percentage of bone marrow blasts, or progression to a more advanced MDS FAB subtype than pretreatment
Relapse after CR or PR	At least 1 of the following: Return to pretreatment bone marrow blast percentage Decrement of $\geq 50\%$ from maximum remission/response levels in granulocytes or platelets Reduction in Hgb concentration by ≥ 1.5 g/dL or transfusion dependence
Cytogenetic response	Complete Disappearance of the chromosomal abnormality without appearance of new ones Partial At least 50% reduction of the chromosomal abnormality
Disease progression	For patients with: Less than 5% blasts: $\geq 50\%$ increase in blasts to $> 5\%$ blasts 5%-10% blasts: $\geq 50\%$ increase to $> 10\%$ blasts 10%-20% blasts: $\geq 50\%$ increase to $> 20\%$ blasts 20%-30% blasts: $\geq 50\%$ increase to $> 30\%$ blasts Any of the following: At least 50% decrement from maximum remission/response in granulocytes or platelets Reduction in Hgb by ≥ 2 g/dL Transfusion dependence
Survival	Endpoints: Overall: death from any cause Event free: failure or death from any cause PFS: disease progression or death from MDS DFS: time to relapse Cause-specific death: death related to MDS

Deletions to IWG response criteria are not shown.

To convert hemoglobin from grams per deciliter to grams per liter, multiply grams per deciliter by 10.

MDS indicates myelodysplastic syndromes; Hgb, hemoglobin; CR, complete remission; HI, hematologic improvement; PR, partial remission; FAB, French-American-British; AML, acute myeloid leukemia; PFS, progression-free survival; DFS, disease-free survival.

*Dysplastic changes should consider the normal range of dysplastic changes (modification).⁴¹

†Modification to IWG response criteria.

‡In some circumstances, protocol therapy may require the initiation of further treatment (eg, consolidation, maintenance) before the 4-week period. Such patients can be included in the response category into which they fit at the time the therapy is started. Transient cytopenias during repeated chemotherapy courses should not be considered as interrupting durability of response, as long as they recover to the improved counts of the previous course.

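### Appendix B lets a blood-count fall or transfusion dependence count as MDS relapse or progression with no link to the disease, so non-relapse cytopenia after transplant could distort 1-year progression, EFS and NRM

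*Combined protocol and SAP*

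**What the plan says.** Section 8.1 lists time to progression, OS, EFS and NRM, all at 1 year, as secondary outcomes. It defines none of progression, EFS or NRM. Section 8.1 and footnote j of the study calendar (Section 7) point to Appendix B for disease assessment.

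The MDS table in Appendix B contains four relevant rows:

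- **Relapse after CR or PR.** One item is enough. Besides a return to the pretreatment blast level, the list has a fall of 50% or more "from maximum remission/response levels in granulocytes or platelets Reduction in Hgb concentration by" 1.5 g/dL or more, or transfusion dependence. (The quote spans two adjacent list items.)
- **Progression.** After the blast thresholds comes a second list, any item of which suffices: "At least 50% decrement from maximum remission/response in granulocytes or platelets", an Hgb fall of 2 g/dL or more, or transfusion dependence.
- **Failure.** "Death during treatment or disease progression characterized by worsening of cytopenias, increase in percentage of bone marrow blasts", or a move to a more advanced subtype.
- **Survival.** "Event free: failure or death from any cause".

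The footnote on transient cytopenia reads "Transient cytopenias during repeated chemotherapy courses should not be considered as interrupting durability of response". It does not mention transplant.

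The CLL table, by contrast, counts a platelet or Hgb fall as progression only when it is a fall "from baseline secondary to CLL". The AML table stops at partial remission (its last entry is "Blasts < 5% if Auer rod positive") and has no relapse row. For AML patients in confirmed remission before infusion, "a bone marrow biopsy and/or aspirate are not required; disease can be followed by confirmatory CBCs".

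**The concern.** Every patient here receives TLI, ATG and TBI, a donor graft, tacrolimus and MMF. After such treatment, counts can fall or transfusions can be needed for reasons other than returning MDS: GVHD, infection, drugs or poor graft function. The MDS rows make no allowance for these causes. An MDS patient in remission whose platelets halve from their best level, with a clean marrow, meets the relapse row as written.

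Three of the secondary estimates depend on who is called relapsed. A count-only event adds to progression. It ends event-free survival early, or creates an EFS event where there was none. If the patient later dies of infection or GVHD, the death follows a recorded relapse and drops out of NRM. These are the figures by which the protocol would judge whether adding TBI keeps the regimen tolerable and controls disease.

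**Working it through.** The documents give no figure for this point, so there is none to reproduce. The check compares the tables and then sets a scale.

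**Step 1. Do the tables treat count falls alike?**

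| Histology (Appendix B) | Relapse or progression category | Can a count fall alone qualify? | Must it be due to the disease? |
|---|---|---|---|
| NHL | Yes | No, lesion or marrow based | Not applicable |
| CLL | Yes | Platelets and Hgb | Yes, stated |
| MDS | Yes | Granulocytes, platelets, Hgb, transfusion dependence | No |
| AML | None | No rule | No rule |
| MPD, CMML (eligible, Section 3.1) | No table | No rule | No rule |

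MDS is the only histology in which a count change qualifies without attribution. Since the CLL table carries the qualifier, its absence for MDS is an inconsistency within the appendix.

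**Step 2. Does anything else close the gap?**

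- The footnote is limited to repeated chemotherapy courses and to the durability of a response.
- The 4-week requirement in the MDS table governs responses, not relapse or progression.
- The limit to patients after CR or PR belongs to the relapse row. The Hgb and transfusion items of the progression row state no prior response and no reference level.
- The adverse event log will not reliably supply a cause, because Section 5.1 does not track laboratory values without clinical consequence unless serious.

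**Step 3. Scale per patient.** With N = 20 (Section 10.3), one patient is 1/20 = 5 percentage points. The shift is up to 5 points, not always 5: a patient who truly relapses or dies within the year is an EFS event anyway.

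**Step 4. Scale for NRM.** The reference 1-year NRM in Section 8 is 6% (95% CI 1 to 28%), and 0.06 × 20 = 1.2, about one patient. Moving one death out of NRM takes it from 1/20 = 5% (exact 95% CI 0.1 to 24.9%) to 0/20 = 0% (0 to 16.8%).

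**Step 5. Illustration on assumed inputs.** The documents give neither the number of MDS patients (m) nor the share of progression-free MDS patients who would meet a count-only criterion (q). Assume true progression of 40%, m from 2 to 8 and q from 10% to 50%. Extra progression events = m × (1 − 0.40) × q.

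- Low end: 2 × 0.60 × 0.10 = 0.12 events. Cohort progression is 40% + 0.12/20 = 40.6%.
- High end: 8 × 0.60 × 0.50 = 2.4 events. Cohort progression is 40% + 2.4/20 = 52.0%.
- Within MDS: 40% + 60% × 0.10 = 46%, up to 40% + 60% × 0.50 = 70%.

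These show how the result depends on m and q. They are not estimates for this trial.

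**The case against.** The strongest reply is that nobody will score these rows mechanically. Section 6 says outcomes come from the transplant database and are reviewed by the investigator and a core group before being finalized. Section 8.1 cites Appendix B for evaluating tumor burden, and footnote j cites it for response assessment. No section adopts the MDS Survival row as the trial's EFS. The Failure row, which feeds that definition, describes disease progression marked by cytopenia rather than bare cytopenia. All of this is fair. It shows that the path from a count fall to EFS and NRM is an inference. It does not supply a rule: where the body defines nothing, Appendix B is the only written standard, and departing from it is unrecorded judgement in an open-label, single-arm study.

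A reader might also infer that MDS patients would be scored as progressing within weeks of conditioning, or after any transfusion. The documents do not support that. The relapse row applies only after a remission or response, its granulocyte and platelet falls are measured from the best level reached, and assessment is typically around Day 90, then at 6 and 12 months as indicated. The table says transfusion dependence, not transfusion. The exposure is mainly to later cytopenia, after counts have recovered.

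**Conclusion.** The point holds as a risk of misclassification, not as a demonstrated error. Followed literally, the MDS rows can count non-relapse cytopenia as relapse or progression. This would overstate 1-year progression, worsen EFS and could understate NRM. The size is up to 5 points per patient. The total is unknown, because the documents give neither the number of MDS patients nor a rate of non-relapse cytopenia or transfusion dependence after this regimen.

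Two stronger readings should be resisted:

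- A loss of 15 to 30 points of EFS (3/20 to 6/20) would need 3 to 6 MDS patients, all misclassified and all otherwise event-free at 1 year. Nothing in the documents supports those inputs.
- The missing AML row might suggest that AML relapses go uncounted and that errors run in opposite directions by disease. The gap leaves AML relapse to judgement; it does not show that relapses are missed.

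Only secondary estimates are exposed, and no test is specified for them. The Day 28 chimerism endpoint, the two-stage decision, the Grade 4 GVHD stopping rule and OS do not depend on these criteria.

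**What to change.** Amend the protocol, with a date, before the secondary outcomes are analysed:

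1. In the MDS table, state: *After HCT, a fall in granulocytes, platelets or Hgb, or transfusion dependence, counts as relapse or progression only with marrow, cytogenetic, molecular or blood-blast evidence of recurrent disease, that is, secondary to MDS.* This mirrors the CLL table.
2. In Section 8.1, define EFS for all histologies as time from Day 0 to relapse or progression or death from any cause, and NRM as death without prior relapse or progression.
3. Supply relapse criteria for AML, MPD and CMML. Hodgkin lymphoma has no table under its own name either, so say which criteria apply.

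The cost is wording and a re-reading of events against the new definitions. There are two drawbacks. Cytopenias with no disease work-up will not count as relapse, and marrow examination is not guaranteed, since footnote j makes it optional and AML in remission may be followed by blood counts. The change also comes after accrual closed (Section 6), so it must be dated and disclosed with the results.
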